10.1.3 CONFIDENTIALITY AND PRIVACY

Participant confidentiality and privacy is strictly held in trust by the participating investigators, their staff, and the sponsor(s) and their interventions. This confidentiality is extended to cover testing of biological samples and genetic tests in addition to the clinical information relating to participants. Therefore, the study protocol, documentation, data, and all other information generated will be held in strict confidence. No information concerning the study or the data will be released to any unauthorized third party without prior written approval of the sponsor.

All research activities will be conducted in as private a setting as possible.

The study monitor, other authorized representatives of the sponsor, representatives of the Institutional Review Board (IRB), regulatory agencies or pharmaceutical company supplying study product may inspect all documents and records required to be maintained by the investigator, including but not limited to, medical records (office, clinic, or hospital) and pharmacy records for the participants in this study. The clinical study site will permit access to such records.

The study participant's contact information will be securely stored at each clinical site for internal use during the study. At the end of the study, all records will continue to be kept in a secure location for as long a period as dictated by the reviewing IRB, Institutional policies, or sponsor requirements.

Study participant research data, which is for purposes of statistical analysis and scientific reporting, will be stored on the Research Electronic Data Capture (REDCap) system managed by Washington University School of Medicine. This will not include the participant's contact or identifying information. Rather, individual participants and their research data will be identified by a unique study identification number. The study data entry and study management systems will be secured and password protected. At the end of the study, all study databases will be de-identified and archived.

10.1.4 FUTURE USE OF STORED SPECIMENS AND DATA

Data collected for this study will be analyzed and stored at Washington University School of Medicine. After the study is completed, the de-identified, archived data will be transmitted to and stored at the National Data Archive, for use by other researchers including those outside of the study.

10.1.6 SAFETY OVERSIGHT

Safety oversight will be performed by an independent safety monitor (ISM). The ISM will be a physician with relevant expertise in the care of postoperative critically ill patients. The ISM will be independent from the study conduct and free of conflict of interest, or measures should be in place to minimize perceived conflict of interest. The ISM will review adverse events as they reported, according to the timelines outlined in section 8.3.5.

In addition to as-needed reviewing of reportable events, the ISM will review safety data every 6 months. This review will include the following safety outcomes described in section 8.2: psychotomimetic side effects, clinical and adverse events checklist, level of sedation, vital signs during study medication infusion, and nausea/vomiting.

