8.3.5 ADVERSE EVENT REPORTING

Adverse events will be reported to the Washington University IRB according to the timeframes set forth by the IRB:

- An event that meets the definition of an unanticipated problem involving risk to participants or others and results in the death of a participant: will be reported within 1 working day.
- An event that meets the definition of an unanticipated problem involving risk to participants or others and does NOT result in the death of a participant: will be reported within 10 working days.
- Adverse events and serious adverse events that do not also meet the definition of an unanticipated problem involving risks to participants or others: will be reported annually during continuing review.
- An unexpected adverse drug event that result in the death of a participant: will be reported within 1 working day.
- An unexpected adverse drug events that does NOT result in the death of a participant: will be reported within 10 working days.

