8.3.6 SERIOUS ADVERSE EVENT REPORTING

The study clinician will immediately report to the sponsor any serious adverse event, whether or not considered study intervention related, including those listed in the protocol or investigator brochure and must include an assessment of whether there is a reasonable possibility that the study intervention caused the event. Study endpoints that are serious adverse events (e.g., all-cause mortality) must be reported in accordance with the protocol unless there is evidence suggesting a causal relationship between the study intervention and the event (e.g., death from anaphylaxis). In that case, the investigator must immediately report the event to the sponsor.

All serious adverse events (SAEs) will be followed until satisfactory resolution or until the site investigator deems the event to be chronic or the participant is stable. Other supporting documentation of the event may be requested by the study sponsor and should be provided as soon as possible.

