8.4 UNANTICIPATED PROBLEMS

8.4.1 DEFINITION OF UNANTICIPATED PROBLEMS (UP)

The Office for Human Research Protections (OHRP) considers unanticipated problems involving risks to participants or others to include, in general, any incident, experience, or outcome that meets all of the following criteria:

- Unexpected in terms of nature, severity, or frequency given (a) the research procedures that are described in the protocol-related documents, such as the Institutional Review Board (IRB)-approved research protocol and informed consent document; and (b) the characteristics of the participant population being studied;
- Related or possibly related to participation in the research (“possibly related” means there is a reasonable possibility that the incident, experience, or outcome may have been caused by the procedures involved in the research); and
- Suggests that the research places participants or others at a greater risk of harm (including physical, psychological, economic, or social harm) than was previously known or recognized.

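### Serious adverse events judged unrelated or expected reach the independent safety monitor only on the IRB's annual timetable, because the immediate report in section 8.3.6 is not routed to the monitor

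*Combined protocol and SAP*

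**What the plan says.** Section 10.1.6 assigns safety oversight to an independent physician monitor. On individual events it says: "The ISM will review adverse events as they reported, according to the timelines outlined in section 8.3.5". It adds a review of safety data every 6 months: "This review will include the following safety outcomes described in section 8.2". The items then named are psychotomimetic effects, the side-effect checklist, sedation, vital signs during infusion, and nausea and vomiting.

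Section 8.3.5 is written for a different recipient: "Adverse events will be reported to the Washington University IRB according to the timeframes set forth by the IRB". Unanticipated problems go within 1 working day if fatal and 10 working days if not. Adverse events and SAEs outside that definition "will be reported annually during continuing review". Two further items set short clocks for drug events: "An unexpected adverse drug event that result in the death of a participant: will be reported within 1 working day", and "An unexpected adverse drug events that does NOT result in the death of a participant: will be reported within 10 working days".

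Section 8.3.6 sets the fastest route, to another recipient: "The study clinician will immediately report to the sponsor any serious adverse event, whether or not considered study intervention related". The ISM is not mentioned there.

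Section 8.4.1 defines an unanticipated problem as "any incident, experience, or outcome that meets all of the following criteria": unexpected, at least possibly related to the research, and suggesting greater risk than was known. Under 8.3.3.3 the principal investigator decides whether an event is expected.

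**The concern.** An independent monitor is there partly to check the study team's judgements on relatedness and expectedness. By borrowing the IRB clocks, section 10.1.6 lets those same judgements decide whether the monitor hears of a serious event within days or at the yearly report. An SAE judged unrelated to study drug, or judged consistent with the described risks, has only the annual clock.

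The setting makes this practical. The cohort behind the accrual estimate in section 5.5 had cardiac, neurosurgical or vascular surgery with an ICU admission, so serious postoperative events are plausible and many will be attributed to surgery. No interim analysis is planned (9.4.6). Section 10.1.2 allows suspension for unacceptable risk, but the ISM cannot contribute to that decision on events it has not received.

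**Working it through.** **Which SAEs have which clock.** Reading 8.3.5 with 8.4.1 and 8.3.3.3, and carrying the clocks over to the ISM as 10.1.6 directs:

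| SAE | Clock |
|---|---|
| Unanticipated problem, fatal | 1 working day |
| Unanticipated problem, not fatal | 10 working days |
| Unexpected adverse drug event, fatal, whether or not an unanticipated problem | 1 working day |
| Unexpected adverse drug event, not fatal, whether or not an unanticipated problem | 10 working days |
| Neither of these: judged unrelated to study drug, or expected in nature, severity and frequency | Annual |

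An unexpected adverse drug event that is not an unanticipated problem fits both the annual item and a short-clock item. I take the shorter clock to govern. The documents do not define an adverse drug event. I take it to exclude events judged unrelated to the drug.

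The gap is therefore the last row. A death falls there if it is judged unrelated. Anaphylaxis is the clearest drug-related example, because section 2.3.1 lists it without qualification.

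**Other routes to the ISM.** The 8.3.6 report covers every SAE at once but names only the sponsor. The 6-monthly review would show a serious event only as far as it appears in the section 8.2 measures. Most of these are taken during the infusion. Nausea and vomiting are asked about at each post-infusion visit, and the checklist is repeated on day 14.

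**When the reviews fall relative to dosing.** Inputs: 307 potentially eligible patients in 6 months, 20% enrolling, and a target of 32 (section 5.5); study duration 1 year (synopsis). Assumption: the 6-month and annual clocks start near first enrolment.

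- The plan's own accrual figure: 307 × 0.20 / 6 = 10.23 per month, against 10 stated. It reproduces.
- Time to enrol 32: 32 / 10 = 3.2 months (32 / 10.23 = 3.13).
- Lag from consent to dosing: the schedule of activities puts consent at day -7 to -1, and section 6.1.2 allows dosing up to postoperative day 3. That is about 10 days at most, so dosing ends at about month 3 to 4.
- Distance from last enrolment to the 6-monthly review: 6 - 3.2 = 2.8 months. To the annual report: 12 - 3.2 = 8.8 months.
- Rate at which enrolment ends exactly at month 6: 32 / 6 = 5.33 per month.
- Rate at which enrolment ends exactly at month 12: 32 / 12 = 2.67 per month.

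| Patients per month | Months to enrol 32 | 6-monthly review | Annual report |
|---|---|---|---|
| 10 (planned) | 3.2 | after dosing | after dosing |
| 5.33 | 6.0 | about the end of dosing | after dosing |
| 2.67 | 12.0 | during dosing (6 × 2.67 = 16 enrolled) | about the end of dosing |

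A rate below 2.67 per month would not complete enrolment within the stated 1-year duration.

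**The case against.** A reader might infer that every SAE that is not an unanticipated problem waits a year. The documents do not support that: 8.3.5 gives unexpected adverse drug events their own 1- and 10-working-day clocks.

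A reader might also infer that any risk named in 2.3.1 is automatically expected. Section 8.3.3.3 makes an event unexpected if its nature, severity or frequency departs from the described risk. Section 2.3.1 says that the study's doses have not been associated with clinically significant blood pressure or heart rate changes, and it ties respiratory depression to overdosage or rapid administration. Serious hypertension or respiratory depression could therefore count as unexpected and go within 10 working days. This narrows the gap but does not close it.

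The 6-monthly review is worded as including certain items, not as limited to them, and sedation and vital signs could reveal some serious events. That stands. It still does not require SAEs or deaths to be shown, and at planned accrual it comes after dosing. The separate mention of as-needed review of reportable events adds no deadline beyond those in 8.3.5.

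It would also be too strong to call the ISM the only safeguard. The sponsor receives every SAE immediately, the IRB receives the short-clock events, and three halted infusions prompt the principal investigator to consider revising the regimen (7.1). That 10.1.7 marks clinical monitoring as not applicable does not show that safety review is absent, and 10.1.8 still refers to monitors. What stands is that none of these routes puts an SAE judged unrelated or expected before the ISM promptly.

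Finally, the timing depends on a clock start that the documents do not give and on a steady 10 patients per month. Section 9.4.2 shows participants enrolled under two protocol versions, which makes uninterrupted accrual less certain.

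**Conclusion.** The gap is real but limited. SAEs, including deaths, that are neither unanticipated problems nor unexpected adverse drug events have only an annual clock to the ISM. The immediate report that would close the gap is addressed to the sponsor alone. This follows from the text and does not depend on accrual.

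Accrual sets the practical consequence. On the assumed clock start, at the planned rate both the 6-monthly review and the annual report come after the last patient is dosed. Between 2.67 and 5.33 per month the 6-monthly review falls during dosing, and only the annual report comes too late to inform it. The documents do not support saying that the ISM sees no serious event until dosing has ended.

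This is a should-fix. The trial is small, each participant has one planned infusion of about 3 hours, and other recipients see SAEs promptly. But the delay is a stated rule and is easily removed.

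**What to change.** In section 10.1.6, replace the reference to the 8.3.5 timelines with an ISM-specific rule: every SAE and every death, whatever its expectedness or relatedness, is sent to the ISM at the same time as the 8.3.6 report to the sponsor. In the same section, add cumulative SAEs and deaths to the listed content of the 6-monthly review. Leave the IRB clocks in 8.3.5 unchanged.

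If the ISM is to see these counts by arm, say so and give the procedure. The Investigational Drug Service holds the randomization scheme (6.3), so it should supply any by-arm listing, to the ISM only, so that the study team stays blinded.

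The cost is one or two sentences and one more recipient for a report that already exists. The ISM will read more reports, many of them ordinary surgical complications. A by-arm listing would add a small task for the Investigational Drug Service.

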10.1.7 CLINICAL MONITORING

Not applicable

10.1.8 QUALITY ASSURANCE AND QUALITY CONTROL

Each clinical site will perform internal quality management of study conduct, data and biological specimen collection, documentation and completion. An individualized quality management plan will be developed to describe a site's quality management.]

Quality control (QC) procedures will be implemented beginning with the data entry system and data QC checks that will be run on the database will be generated. Any missing data or data anomalies will be communicated to the site(s) for clarification/resolution.

Following written Standard Operating Procedures (SOPs), the monitors will verify that the clinical trial is conducted and data are generated and biological specimens are collected, documented (recorded), and reported in compliance with the protocol, International Conference on Harmonisation Good Clinical Practice (ICH GCP), and applicable regulatory requirements (e.g., Good Laboratory Practices (GLP), Good Manufacturing Practices (GMP)).

The investigational site will provide direct access to all trial related sites, source data/documents, and reports for the purpose of monitoring and auditing by the sponsor, and inspection by local and regulatory authorities.

10.1.9 DATA HANDLING AND RECORD KEEPING

10.1.9.1 DATA COLLECTION AND MANAGEMENT RESPONSIBILITIES

Data collection is the responsibility of the clinical trial staff at the site under the supervision of the site investigator. The investigator is responsible for ensuring the accuracy, completeness, legibility, and timeliness of the data reported.

All source documents should be completed in a neat, legible manner to ensure accurate interpretation of data.

Hardcopies of the study visit worksheets will be provided for use as source document worksheets for recording data for each participant enrolled in the study. Data recorded in the electronic case report form (eCRF) derived from source documents should be consistent with the data recorded on the source documents.

Clinical data (including adverse events (AEs), concomitant medications, and expected adverse reactions data) and clinical laboratory data will be entered into REDCap, a 21 CFR Part 11-compliant data capture system provided by Washington University School of Medicine. The data system includes password protection and internal quality checks, such as automatic range checks, to identify data that appear inconsistent, incomplete, or inaccurate. Clinical data will be entered directly from the source documents.

10.1.9.2 STUDY RECORDS RETENTION

Study documents should be retained for a minimum of 3 years. These documents should be retained for a longer period, however, if required by local regulations.

10.1.10 PROTOCOL DEVIATIONS

A protocol deviation is any noncompliance with the clinical trial protocol, International Conference on Harmonisation Good Clinical Practice (ICH GCP), or Manual of Procedures (MOP) requirements. The noncompliance may be either on the part of the participant, the investigator, or the study site staff. As a result of deviations, corrective actions are to be developed by the site and implemented promptly.

These practices are consistent with ICH GCP:

- 4.5 Compliance with Protocol, sections 4.5.1, 4.5.2, and 4.5.3
- 5.1 Quality Assurance and Quality Control, section 5.1.1
- 5.20 Noncompliance, sections 5.20.1, and 5.20.2.

It is the responsibility of the site investigator to use continuous vigilance to identify and report deviations within 10 working days of identification of the protocol deviation, or within 10 working days of the scheduled protocol-required activity. All deviations must be addressed in study source documents and reported to the funding agency. Protocol deviations must be sent to the reviewing Institutional Review Board (IRB) per their policies. The site investigator is responsible for knowing and adhering to the reviewing IRB requirements. Further details about the handling of protocol deviations will be included in the MOP.

10.1.11 PUBLICATION AND DATA SHARING POLICY

This study will be conducted in accordance with the following publication and data sharing policies and regulations:

National Institutes of Health (NIH) Public Access Policy, which ensures that the public has access to the published results of NIH funded research. It requires scientists to submit final peer-reviewed journal manuscripts that arise from NIH funds to the digital archive [PubMed Central](#) upon acceptance for publication.

This study will comply with the NIH Data Sharing Policy and Policy on the Dissemination of NIH-Funded Clinical Trial Information and the Clinical Trials Registration and Results Information Submission rule. As such, this trial will be registered at ClinicalTrials.gov, and results information from this trial will be submitted to ClinicalTrials.gov. In addition, every attempt will be made to publish results in peer-reviewed journals. Data from this study may be requested from other researchers 2 years after the completion of the primary endpoint by contacting the principal investigator.

10.1.12 CONFLICT OF INTEREST POLICY

The independence of this study from any actual or perceived influence, such as by the pharmaceutical industry, is critical. Therefore, any actual conflict of interest of persons who have a role in the design, conduct, analysis, publication, or any aspect of this trial will be disclosed and managed. Furthermore, persons who have a perceived conflict of interest will be required to have such conflicts managed in a way that is appropriate to their participation in the design and conduct of this trial.

10.2 ADDITIONAL CONSIDERATIONS

Not applicable

10.3 ABBREVIATIONS

AE	Adverse Event
AUDIT	Alcohol Use Disorders Identification Test
BJH	Barnes-Jewish Hospital
BMI	Body Mass Index
BPRS	Brief Psychiatric Rating Scale
CADSS	Clinical Administered Dissociative State Scale
CFR	Code of Federal Regulations
CGI	Clinical Global Impression
CMP	Clinical Monitoring Plan
CONSORT	Consolidated Standards of Reporting Trials
CPAP	Center for Preoperative Assessment and Planning
CRF	Case Report Form
CTQ	Childhood Trauma Questionnaire
DAST	Drug Abuse Screening Test
eCRF	Electronic Case Report Forms
EEG	Electroencephalogram
FDA	Food and Drug Administration
GABA	Gamma-Aminobutyric Acid
GCP	Good Clinical Practice
GLP	Good Laboratory Practices
GMP	Good Manufacturing Practices
HIPAA	Health Insurance Portability and Accountability Act
ICD	International Classification of Disease
ICH	International Conference on Harmonisation
ICMJE	International Committee of Medical Journal Editors
ICU	Intensive Care Unit
IND	Investigational New Drug Application
IRB	Institutional Review Board
ISM	Independent Safety Monitor
K-PASS	Ketamine for Postoperative Avoidance of Depressive Symptoms
MADRS	Montgomery-Asberg Depression Rating Scale
MedDRA	Medical Dictionary for Regulatory Activities
MOP	Manual of Procedures
NIH	National Institutes of Health
NMDA	N-Methyl-D-Aspartate
OHRP	Office for Human Research Protections
PACU	Post Anesthesia Care Unit
PHQ-9	Patient Health Questionnaire-9
PI	Principal Investigator
QA	Quality Assurance
QC	Quality Control
QIDS	Quick Inventory of Depressive Symptomatology
RASS	Richmond Agitation and Sedation Scale
REDCap	Research Electronic Data Capture
SAE	Serious Adverse Event
SOA	Schedule of Activities
SOP	Standard Operating Procedure
SWA	Slow Wave Activity

UP	Unanticipated Problem
US	United States

